3. To identify clinic-level barriers to adoption and implementation of 3HP under each delivery strategy.
4. To determine the proportion of patients for whom 3HP treatment is discontinued due to adverse events/intolerance.
5. To determine the cumulative 16-month incidence of active TB in each arm.
6. To determine the cumulative 28-month incidence of active TB in each arm.

Study Design:

Participants will be randomized to one of three arms to receive latent tuberculosis infection (**LTBI**) treatment with once weekly isoniazid (INH) and rifapentine (RPT) for 12 weeks given by either facilitated DOT, facilitated SAT, or an informed choice between DOT and SAT (with the assistance of a decision aid tool).

Study Agents:

Participants in all arms will receive the following medications approved for TB preventive therapy by the World Health Organization (**WHO**):

- RPT 900 mg and INH 900 mg once-weekly x 12 doses
- Pyridoxine (vitamin B₆) 50 mg offered once weekly, as recommended for 3HP, to protect against isoniazid-related peripheral neuropathy

Study Population/Sample Size:

We will enroll 1656 PLHIV (552/arm) aged 18 years and above accessing HIV/AIDS care at the Mulago Immune Suppression Syndrome Clinic who meet all study inclusion criteria and none of the exclusion criteria.

Outcomes:

1. Primary Outcome:

- The proportion of eligible participants who accept treatment and take at least 11 of 12 once weekly doses of RPT/INH within 16 weeks of treatment initiation.

2. Secondary Outcomes categorized using the RE-AIM framework:

RE-AIM Domain	Outcome
Reach	
 • Proportion of eligible PLHIV offered 3HP who accept to initiate treatment (by age, gender, CD4 stratum, viral load suppression).
Effectiveness/ Cost-effectiveness	
 • Incremental cost of each delivery strategy per disability adjusted life year (DALY) averted. • The incremental health system cost per DALY averted. • The incremental patient cost per DALY averted. • Proportion of participants who initiate 3HP for whom treatment is discontinued due to adverse events or intolerance. • Cumulative 16-month incidence of active TB. • Cumulative 28-month incidence of active TB.

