^a 3HP treatment may last up to 16 weeks^b Patients randomized to choice arm only^c Time-and-motion studies will be performed on 40 randomly selected days (one day per week throughout the year, stratified by day of week). We anticipate that this will capture up to 250 unique participant visits per arm (750 total).^d Patient costing surveys will include 50 participants from each arm, or 150 participants total^e Only if symptomatic, except at end of follow-up.^f 24 participants/arm

Outcome Measures

Primary Outcome (Effectiveness of delivery options)

Outcome	Numerator	Denominator
Proportion accepting and completing 3HP treatment	Number who take at least 11 of 12 doses within 16 weeks of treatment initiation	Number randomized

Secondary Outcomes (Quantitative)

Outcome	Numerator	Denominator
REACH		
Treatment acceptance	Number taking at least one dose of 3HP	Number randomized
EFFECTIVENESS		
Treatment completion	Number who take at least 11 of 12 doses within 16 weeks of treatment initiation	Number taking at least one dose of 3HP

Cost-effectiveness (overall)	(Cost in Arm A – cost in Arm B) from societal perspective	(DALYs averted in Arm A – DALYs averted in Arm B) from societal perspective
Cost-effectiveness (health system)	As above, but from health system/provider perspective	As above, but from health system/provider perspective
Cost-effectiveness (patient)	As above, but from patient perspective	As above, but from patient perspective
Safety	Number for whom treatment discontinued due to adverse events or intolerance.	Number taking at least one dose of 3HP
Cumulative incidence of TB at 16 months	Number diagnosed with TB during 16-month follow-up	Risk set*
Cumulative incidence of TB at 28 months	Number diagnosed with TB during 28-month follow-up	Risk set*
ADOPTION		
All Participants		
Visit Cost Reimbursement	Number of visits for which reimbursement provided on same day	Total number of DOT/refill visits
Time to complete clinic visit	Mean and median number of minutes for each DOT/refill visit	--
SMS or IVR phone call reminders delivered	Number of SMS or IVR phone call dosing or clinic visit reminders delivered	Total number of SMS reminders scheduled to be sent
SMS or IVR phone call reminders following missed appointments	Number of SMS or IVR phone call dosing or clinic missed appointment reminders delivered	Number of participant weeks with 3HP missed appointments
Screening for active TB	Number screened for active TB during DOT visits	Total number of DOT visits

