Screening for side effects	Number screened for side effects during DOT visits	Total number of DOT visits
Participants taking 3HP by SAT only		
Dosing confirmation via 99DOTS	Number of doses recorded by 99DOTS	Total number of scheduled doses (not including doses taken during clinic visits).
SMS or IVR phone call missed dose reminders delivered	Number of SMS or IVR phone call missed dose reminders delivered	Number of participant weeks with 3HP dosing not recorded by 99DOTS
SMS or IVR phone call weekly check-in delivered	Number of weekly SMS or IVR phone call check-ins delivered	Number of participant weeks taking 3HP (not including weeks where dosing is directly observed)

Follow up (phone calls or home visits) for negative response to weekly SMS or IVR phone call check-in	Number of follow-up calls and/or home visits completed following negative response to weekly SMS or IVR phone call check-in message	Number of participant weeks of negative response to weekly SMS or IVR phone call check-in messages
IMPLEMENTATION		
Costs of preventive services	Mean total patient costs related to TB preventive care services	
Participant satisfaction	Mean score on PSQ questionnaire	--
Barriers to 3HP delivery	Thematic interpretation of provider- and clinic-level barriers to care from provider focus group discussions	
Barriers to 3HP completion	Thematic interpretation of barriers to 3HP completion from patient interviews	

* Participants will be censored at the time of active TB diagnosis or treatment initiation, death, loss to follow-up (*i.e.*, unable to be contacted and have sputum collected between 10 and 28 months after 3HP treatment discontinuation or completion), or end of the 28-month post-treatment follow-up period

Statistical Considerations

1. Primary hypotheses:

- a. The proportion who accept and complete 3HP will be highest among PLHIV randomized to the informed choice arm.
- b. The proportion of PLHIV who accept and complete 3HP can exceed 80% in a high HIV/TB burden setting.

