- **Primary outcome** analysis will include: 1) unadjusted intent-to-treat comparisons of effectiveness between arms and 2) simple calculation (using the exact binomial confidence intervals) of the effectiveness of each delivery option, with a target of 80%. In these analyses, participants randomized to the choice arm will be treated separately from those randomized to either facilitated DOT or facilitated SAT; the proportion of those in the patient choice arm who choose DOT or SAT will be measured, but the primary outcome will consider all individuals in this arm as randomized to patient choice. Whether 80% acceptance and completion is achieved will be based on the lower bound of the Bonferroni-corrected 98.3% confidence interval exceeding 0.80 in any of the three arms. The intent-to-treat comparisons will use log-binomial regression to calculate prevalence ratios, and Fisher's exact test to determine statistical significance (two-sided alpha of 0.025, including Bonferroni correction). Participants who decline to initiate 3HP after randomization will be counted as not accepting/completing treatment in the primary (intent-to-treat) analysis and will be followed over time for clinical outcomes.
- **Secondary outcome** analysis will include:
 1. **Reach outcomes:** Analysis will include 1) unadjusted comparisons across arms, 2) per protocol analysis of DOT versus SAT in the choice arm in case of crossover including analysis of outcomes among participants who crossed over against outcomes among those who stayed in their originally selected strategy if a sufficiently large number of patients cross over from DOT to SAT or vice versa and 3) simple calculation of the proportion of patients offered 3HP who accept treatment in each arm. We will also compare this outcome across key demographic variables including age, gender, CD4 stratum, and viral load suppression.
 2. **Effectiveness outcomes:** Analysis of effectiveness outcomes will include the development of TB and the occurrence of adverse events analyzed with Chi-square tests, logistic regression, Kaplan-Meier curves, log-rank tests, and Cox regression methods as appropriate. Any signs or symptoms lasting ≥ 3 days duration (by patient self-report) during the previous month will be recorded and included in our analysis. We will also compare outcomes across key demographic variables including age and gender.

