### 3.7 Analysis of secondary outcomes

Secondary outcome analysis will include:

1. **Reach outcome(s):** 1) Unadjusted comparisons across arms, and 2) simple calculation of the proportion of patients randomized who accept treatment in each arm.
2. **Effectiveness outcomes:** 1) Occurrence of AEs across arms will be assessed using Chi-square tests and logistic regression; 2) Incidence of active TB will be assessed using Kaplan-Meier curves, log-rank tests, and Cox proportional hazards methods as appropriate. Assessment for active TB occurs at 15-16 months post enrolment. Survival analyses will include:
  - o An assessment of the incidence rate of TB, comparing across arms (DOT vs. SAT vs. Choice) using Kaplan Meier, time-to-event analyses. We will estimate the difference in the Kaplan Meier and Cox proportional hazard estimators for the survivor functions, comparing the arms to get hazard ratios and 95% CIs.
  - o An assessment of the incidence rate per arm by drug compliance, which will include for each arm: a comparison of the incidence of active TB in those within the arm that complete at least 11 of the 12 doses within the allotted 16 weeks vs. the incidence of active TB in those within the arm that complete  $\leq$ 10 doses of 3HP. We will estimate the difference in the Kaplan Meier and Cox proportional hazard estimators for the survivor functions, comparing the arms to get hazard ratios and 95% CIs.

3. **Adoption outcomes:** For each process metric, we will report the monthly proportion (and 95% CI) number, or median (interquartile range (IQR)) to assess the implementation of intervention components in each arm.
4. **Implementation outcomes:** Quantitative data will be assessed using multivariable regression models to compare by study arm patient survey data including a) patient costs; b) scores on questions related to patient barriers to TB preventative care; and c) patient satisfaction. Qualitative data will be analysed using appropriate software where open coding will be applied to generate codes and themes. Thematic groupings will be developed and reviewed to identify emergent themes within each domain of the coding framework and quotes that best represent each domain. Thematic interpretation will include collaborative development of a coding framework and detailed coding of transcripts.

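### Each arm's cumulative TB incidence would be slightly overstated if reported as one minus Kaplan-Meier with deaths censored; treat death as a competing event

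*Protocol*

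**What the plan says.** The targets are absolute risks. In the Protocol Synopsis, secondary objective 5 is "To determine the cumulative 16-month incidence of active TB in each arm" and objective 6 is "To determine the cumulative 28-month incidence of active TB in each arm". The SAP's own list of objectives (section 2.1) contains the 16-month objective only.

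The outcome table in the protocol (Outcome Measures) sets the 28-month numerator as "Number diagnosed with TB during 28-month follow-up" and gives the risk set as the denominator. The risk set is defined only by a footnote: "Participants will be censored at the time of active TB diagnosis or treatment initiation, death, loss to follow-up", or the end of follow-up.

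On method, the protocol's Data Analysis section covers TB and adverse events together with "Chi-square tests, logistic regression, Kaplan-Meier curves, log-rank tests, and Cox regression methods as appropriate". The SAP separates the two. Adverse events get chi-square tests and logistic regression, and for TB "Incidence of active TB will be assessed using Kaplan-Meier curves, log-rank tests, and Cox proportional hazards methods as appropriate". Its described output is a contrast, "comparing the arms to get hazard ratios and 95% CIs". SAP section 2.3 says that the SAP prevails over the protocol, but the SAP has no censoring rule of its own. Neither document names a competing-risk estimator, a composite of TB and death, or an estimand that sets death aside.

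**The concern.** A participant who dies without TB cannot develop it later. Kaplan-Meier treats a censored participant as someone who would have gone on to the event at the same rate as those still observed. With deaths censored, one minus Kaplan-Meier therefore estimates the TB risk in a hypothetical cohort in which nobody dies. It does not estimate the share of the arm that develops TB by month 16 or 28, which is what the objectives ask for. The two agree only if no death precedes a TB diagnosis. Otherwise the Kaplan-Meier figure is the higher, and the gap widens with follow-up.

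At stake is the accuracy of a planned secondary estimate: the absolute TB risk reported for each arm. A hazard ratio cannot stand in for it.

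**Working it through.** There is no figure in the plan to reproduce: the documents give no expected TB incidence, TB event count, TB power or death rate. The size has to be worked out under assumptions.

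**Inputs.** From the documents: arm size ("We will enroll 1656 PLHIV (552/arm) aged 18 years and above"), horizons T = 16/12 and 28/12 years, and death as a censoring event. Assumed: constant TB hazard λ of 0.5 to 4 per 100 person-years and constant death hazard μ of 0.5 to 5 per 100 person-years.

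**Formulas.**
- One minus Kaplan-Meier, deaths censored: 1 − exp(−λT)
- Aalen-Johansen cumulative incidence: λ/(λ+μ) × [1 − exp(−(λ+μ)T)]
- Approximate 95% half-width for one arm: 1.96 × √[p(1−p)/552]

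**One case in full** (λ = 0.01, μ = 0.02, 28 months).
- Kaplan-Meier: 1 − exp(−0.02333) = 2.306%.
- Aalen-Johansen: (0.01/0.03) × [1 − exp(−0.07)] = 2.254%.
- Excess: 0.053 points, or 2.3% relative.
- Half-width at 2.306%: 1.25 points.

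| Horizon | TB, death per 100 PY | 1 − KM | Aalen-Johansen | Excess (points) | Relative | Half-width (points) |
|---|---|---|---|---|---|---|
| 16 months | 1, 2 | 1.324% | 1.307% | 0.017 | 1.3% | 0.95 |
| 16 months | 1, 5 | 1.324% | 1.281% | 0.043 | 3.4% | 0.95 |
| 28 months | 1, 2 | 2.306% | 2.254% | 0.053 | 2.3% | 1.25 |
| 28 months | 1, 5 | 2.306% | 2.177% | 0.129 | 5.9% | 1.25 |
| 28 months | 4, 5 | 8.911% | 8.418% | 0.493 | 5.9% | 2.38 |

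Over the whole grid the excess is 0.002 to 0.17 points at 16 months (0.3% to 3.4% relative) and 0.007 to 0.49 points at 28 months (0.6% to 5.9%). At TB 1 and death 2 it is 2% to 4% of the half-width (0.017/0.95 and 0.053/1.25). At the extreme corner it is 0.493/2.38 = 21%.

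**Detection late in the window.** Constant hazards may understate the gap. The SAP places TB assessment at 15 to 16 months after enrolment, and the protocol asks all undiagnosed participants for sputum at 28 months whatever their symptoms. If all TB were found at the final visit, the ratio of the two estimates would reach its ceiling, exp(μT). For μ from 0.005 to 0.05 that is an excess of 0.7% to 6.9% at 16 months and 1.2% to 12.4% at 28 months. As counts: with 552 in an arm, 15 deaths and then 12 TB cases at the last visit, Kaplan-Meier gives 12/537 = 2.235% and Aalen-Johansen 12/552 = 2.174%. At the worst corner (TB 4, death 5, 28 months) the ceiling is 8.911% against 8.911/1.1237 = 7.930%. That is 0.98 points, or 41% of the 2.38-point half-width.

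**Finite samples.** In 1,000 simulated arms of 552 at each of three settings, one minus Kaplan-Meier was never below Aalen-Johansen. The mean excesses were 0.017 points (16 months; TB 1, death 2), 0.053 points (28 months; same rates) and 0.153 points (28 months; TB 2, death 3).

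**Contrast between arms at 28 months.** With TB at 2 versus 1 and death at 2 per 100 person-years in both arms, the risk ratio is 1.977 by either method. With equal TB hazards and death at 1 versus 3, the Kaplan-Meier ratio is 1 and the Aalen-Johansen ratio 1.023.

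**The case against.** The strongest reply is that the plan never says outright that the per-arm figure is one minus Kaplan-Meier. The outcome table gives a count over a risk set, and the footnote lists TB diagnosis, the event itself, among the reasons for censoring. It can therefore be read as a rule for when a participant leaves the risk set, which is the right rule for hazards and rates. The methods are also listed for use as appropriate, and the SAP speaks of incidence rates and hazard ratios. This stands as far as it goes, and it is why the point is conditional. It does not remove the point. The objectives ask for a cumulative incidence, and Kaplan-Meier is the only absolute-risk method the controlling document names for TB. If the dead were instead dropped from a simple denominator, the result would err the same way, as 12/537 against 12/552 shows.

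The reply also holds that the effect is negligible. At TB 1 and death 2 per 100 person-years the excess amounts to about 0.1 of a participant per arm at 16 months (0.017% × 552) and 0.3 at 28 months (0.053% × 552). That stands, and it sets the severity. It is also correct that the 28-month analysis rests on the protocol alone.

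**Conclusion.** The point holds as a low-severity improvement. If followed in the most direct way, the plan gives per-arm TB risks that are too high, by a few percent in relative terms under the assumed rates and at most about 7% (16 months) or 12% (28 months) if all detection falls at the final visit. The direction is certain once any death precedes a TB diagnosis. The size rests on assumed mortality and TB rates, and stays within the sampling error of an arm of 552 throughout the range examined.

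A reader might infer three stronger things, none of which the documents support.
- *A stated incidence is wrong.* No TB incidence is stated anywhere; this concerns an estimate still to be made.
- *The comparison of arms is biased.* Log-rank and Cox with deaths censored are valid for the cause-specific hazard, so the hazard ratios planned in SAP section 3.7 stand. The primary outcome is acceptance and completion of 3HP and is untouched.
- *The cost-utility model inherits the error.* The protocol calibrates that model to people living with HIV in Uganda and does not say that the arms' Kaplan-Meier risks are inputs. A model that applies mortality itself would need cause-specific rates in any case.

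**What to change.** In SAP section 3.7, item 2, and in the protocol's risk-set footnote:

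- Define death without TB as a competing event rather than as censoring for the cumulative incidence.
- Report each arm's 16- and 28-month cumulative incidence by the Aalen-Johansen method with 95% confidence intervals, and state that this is the figure answering objectives 5 and 6. Add the 28-month outcome to the SAP.
- Report the number of deaths by arm.
- Keep log-rank and Cox, labelled as cause-specific comparisons. Gray's test is optional.

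While the footnote is open, reconcile three related points. TB diagnosis should be named as the event, not as censoring. The footnote counts 28 months from the end of treatment, whereas the Post-3HP treatment section counts up to 28 months from enrolment. Loss to follow-up is also defined differently in those two places.

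The cost is a few sentences of SAP and protocol wording and one extra event code. The estimator is standard, and death dates are already needed for the censoring rule. No new data, visits or participants are required.

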4. **Patient Costing:** To estimate any additional patient-level and societal costs of 3HP (e.g., ancillary healthcare visits, patient and caregiver costs associated with 3HP, use of formal social support programs), the time-and-motion studies will be supplemented by a patient costing survey (N=150, or 50 participants per arm).

Post-3HP treatment

All participants will be aggressively traced and asked to return to clinic (reimbursed in the usual fashion) after completion of their final medication dose, or at 16 weeks post-treatment initiation (for participants not completing treatment).

The following *routine TB preventive care activities* will be performed by Mulago ISS clinic staff during a routine HIV/AIDS care clinic visit:

Follow-up assessment: Participants will be screened for active TB for a period of two years after 3HP treatment completion (*i.e.*, up to 28 months after enrollment) at clinic visits for routine HIV/AIDS care. TB screening will include symptom assessment using the WHO four-symptom TB screen administered at every visit. For patients with new or progressive TB symptoms a chest X-ray (**CXR**) and sputum for Xpert MTB/RIF and mycobacterial culture will be performed, as per routine WHO and NTLP recommended procedures. Sputum will be induced, if needed. All participants diagnosed with TB at any time point will have sputum submitted for culture and drug susceptibility testing on liquid media. Loss to follow-up will be defined as a participant not able to be contacted and does not return to clinic within the 12-month post treatment follow-up period. At 28 months only, all clients who have not already been diagnosed with TB at any point during follow-up and regardless of any symptoms of TB will be asked to return to the clinic and submit sputum for Xpert MTB/RIF and mycobacterial culture for those with RIF resistance detected via Xpert MTB/RIF.

The following *study-specific activities* will be performed by research staff after 3HP treatment is complete:

1. **Survey 3:** Research staff will administer a survey to document the reason for treatment discontinuation (completed therapy, adverse event/intolerance, other) and to assess satisfaction with TB preventive care received. Study staff will use patient telephone numbers and addresses to contact study participants. If returning to clinic is not possible, the survey may be conducted over the phone.

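### The TB risk-set footnote keeps a participant with one qualifying early contact at risk to the end, so unscreened months can count as TB-free and bias TB incidence, a secondary outcome, downward

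*Protocol*

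**What the plan says.** The Protocol's table of secondary outcomes (Outcome Measures) gives a risk set as the denominator for TB incidence at 16 and 28 months. Its footnote lists the reasons for leaving that set: "Participants will be censored at the time of active TB diagnosis or treatment initiation, death, loss to follow-up", or "end of the 28-month post-treatment follow-up period". Loss is defined there as being "unable to be contacted and have sputum collected between 10 and 28 months after 3HP treatment discontinuation or completion".

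The follow-up assessment text (Post-3HP treatment) defines loss differently, as "a participant not able to be contacted and does not return to clinic within the 12-month post treatment follow-up period", with no sputum condition. It runs TB screening for two years after treatment, which it equates with "up to 28 months after enrollment".

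On detection, the same text says that "TB screening will include symptom assessment using the WHO four-symptom TB screen administered at every visit". The note to Figure 1 places visits every 2 to 3 months. Table 2, footnote e, limits active TB assessment to symptomatic participants except at the end of follow-up, when everyone not yet diagnosed is asked for sputum.

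SAP 3.7(2) plans "An assessment of the incidence rate of TB, comparing across arms (DOT vs. SAT vs. Choice) using Kaplan Meier, time-to-event analyses". It places the TB assessment 15 to 16 months after enrolment, contains no 28-month analysis, and gives neither a loss definition nor a censoring rule. SAP 2.3 gives the SAP precedence, but on this point it is silent.

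**The concern.** Kaplan-Meier, log-rank and Cox methods treat time in the risk set as time in which an event would have been recorded. Here TB is found at clinic visits or at the 28-month sputum, yet nothing ends risk time at the last visit or last negative screen. Loss is all-or-nothing over a long window: one qualifying contact clears it, and the next exit is the end of follow-up. A participant assessed once early in the window and never again therefore contributes many months in which no TB could be seen.

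If TB in those months stays unknown to the study, incidence comes out too low. If retention differs between arms, part of that difference appears as a difference in TB. The wording also leaves analysts to choose the censoring date for those who are lost, so the same data can give different answers.

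**Working it through.** The documents give no TB rate, attrition rate or power for TB incidence, so there is no planned figure to reproduce. The inputs are the dates above. Attrition and TB rates are assumptions.

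**1. Clocks** (30.4375 days per month). Twelve weekly doses take at least 11 weeks (2.53 months), and treatment may last 16 weeks (3.68 months).
- The window opens 10 + 2.53 = 12.5 to 10 + 3.68 = 13.7 months after enrolment. The SAP's 15 to 16 month assessment falls inside it.
- The footnote's end is 28 + 2.53 = 30.5 to 28 + 3.68 = 31.7 months after enrolment, 2.5 to 3.7 months after planned screening stops.
- Two years after treatment is 26.5 to 27.7 months after enrolment, which agrees with the follow-up text and not with the footnote.
- After one contact as the window opens, the unscreened tail is up to 18 months to the footnote's end, 14.3 to 15.5 months to month 28, and 2.3 to 3.5 months to month 16.

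**2. Who is carried forward**
- Natural reading of the footnote: retention needs contact and sputum. Someone with sputum taken early in the window who then disappears is carried to the end. Someone seen without sputum is lost, at an unstated date.
- Looser reading (lost only if both contact and sputum fail): any contact in the window is enough.
- Follow-up text: any contact or return in the 12 months after treatment is enough.

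**3. Unobserved share of counted time.** Let attrition be constant at h per year, with T = 16/12 or 28/12 years from enrolment and window opening s = 12.53/12 or 13.68/12 years. Assume that TB after departure goes unrecorded and that TB hazard is low and constant. The rate is then understated by the unobserved share.
- Observed time: O = (1 − exp(−hT))/h.
- Lower case (those leaving before s are censored on leaving, later leavers are carried to T): C = (1 − exp(−hs))/h + exp(−hs)(T − s).
- Upper bound (every drop-out is carried to T): C = T.
- Unobserved share: 1 − O/C.

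Example, h = 0.10 and T = 28 months: O = 2.081 years. With s = 13.68 months, C = 2.142 and the share is 2.8%. With s = 12.53 months, C = 2.153 and the share is 3.3%. At the upper bound, C = 2.333 and the share is 10.8%.

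| h per year | 28 months, lower case | 28 months, upper bound | 16 months, lower case | 16 months, upper bound |
|---|---|---|---|---|
| 5% | 1.5–1.7% | 5.6% | 0.07–0.16% | 3.3% |
| 10% | 2.8–3.3% | 10.8% | 0.13–0.30% | 6.4% |
| 15% | 4.1–4.8% | 15.6% | 0.19–0.44% | 9.4% |

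**4. Between arms.** Take 5% attrition in one arm, 15% in another and the same true TB rate. The apparent 28-month rate ratio is the ratio of observed fractions: 0.959/0.985 = 0.97 in the lower case (s = 13.68) and 0.844/0.944 = 0.89 at the upper bound.

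**5. Cross-check and test of the remedy.** If a fraction f is last assessed at 13.7 months, the relative understatement at 28 months is close to f × 14.3/28. That is 5.1% for f = 10% and 10.2% for f = 20%. With an assumed TB hazard of 1 per 100 person-years, the true 28-month risk is 2.31%, and the literal rule gives 2.19% and 2.07%. In a simulation of 400,000 participants, censoring at the last assessment returned 2.31% and 2.34%, within simulation error of the truth.

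**The case against.** The strongest reply is that the footnote asks for sputum as well as contact. Before the end of follow-up, sputum is taken only from symptomatic participants, so an asymptomatic participant who attends once, for example 11 months after treatment, and then vanishes is lost on the natural reading. A reader might infer that anyone seen once in the window can never be lost. The documents support that only on the looser reading or under the follow-up text. On the natural reading fewer people are carried forward than the lower case assumes. This part of the reply stands.

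A second reply is that a window defines who is lost, not when they are censored, and an analyst might well use the last visit. That is fair for people classed as lost. It does not help those who are not lost, whom the footnote keeps in the risk set to the end.

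Third, the arms differ in delivery only during treatment. Afterwards all follow the same routine visits and the same 28-month recall, and enrolment screens for intention to stay nearby or in care. Threefold different attrition is therefore an illustration with no basis in the documents.

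Finally, if people who leave come back because they have TB, some of that TB is recorded after all, and the downward bias shrinks.

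**Conclusion.** The gap is real and modest. Followed literally, the footnote counts time with no TB assessment as TB-free, and neither the follow-up text nor the SAP corrects it. With assumed attrition of 5 to 15% per year, the unobserved share is about 1.5 to 5% of counted 28-month time and under 0.5% at 16 months when only those leaving inside the window are carried forward.

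A reader might take the upper-bound figures (6 to 16% at 28 months, 3 to 9% at 16 months, a spurious ratio of 0.89) as the expected effect. They require every drop-out from enrolment onward to be carried to the end, which the footnote does not state. Nor do the documents show that incidence will be understated: that needs both such drop-outs and TB that the study never learns of, and neither rate is given.

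For scale, at 1 TB case per 100 person-years an arm of 552 expects 552 × 0.0231 = 12.7 cases by 28 months, so 5% is about 0.6 of a case. These are secondary outcomes and the primary outcome is not touched. The change is still worth making: the present wording permits several answers from the same data, and a better rule costs little.

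**What to change.** In the risk-set footnote and SAP 3.7(2), use one definition of loss and one clock, and state:

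- Participants without TB are censored at the date of their last documented TB assessment (symptom screen at a visit, or sputum result), or at the nominal 16- or 28-month date if assessed then.
- Only participants with a 28-month sputum result enter the denominator for TB detected by that universal screen.

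A clock that starts at randomization would also cover participants who decline 3HP. They are followed for clinical outcomes but have no end of treatment from which to count.

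The cost is a few sentences, and the rule should need only visit and result dates already recorded. The downsides are slightly less person-time, slightly wider intervals, and a possible small upward bias if people who leave return only because they develop TB. A sensitivity analysis that varies the censoring date, reported by arm, can check the last point.
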